## **Data Collection and Variables**

**Research Associates Training and Certification.** Training for Research Associates (RA), who will be masters prepared, will include interviewing over the telephone, asking sensitive questions, use of study instruments, five practice interviews, and a final certifying audiotaped interview with a volunteer participant. The investigators and each RA rate responses on three mock interviews to determine inter-rater reliability. RAs will be evaluated on their conduct during data collection interviews. The Researcher Evaluation Form is scored by the investigators using recorded calls. Scores are determined by 1) those things executed (e.g., asks questions as written, probes consistently and only when necessary) and 2) negative items (e.g., volunteers personal information that may bias answers, uses directional probes), with 100 being a perfect score and 90 being acceptable. After training, periodic checks of RA performance are conducted.

**Data Collection.** Data collection will occur at baseline, 3, and 6 months post randomization by telephone. All calls are recorded. Data collection takes approximately 45 minutes, based on our current telephone data collection with caregivers and OEF/OIF/OND spouses, using the same and similar instruments. We send response cards to the participant to make answering more efficient. The same masked RA performs all data collection for a participant.

Measures (shown below) were specifically chosen 1) to capture the mechanisms of action related to the theoretical model for individual stress process, and 2) to map onto measures being used by DoD and VHA clinicians and researchers to provide maximum utility and generalizability for the study results. Independent measures have been selected to characterize the study sample and to assess factors that have potential to impact the outcome measures. Many of the instruments and concepts are used in the Rand study of military caregivers (23), or were developed for use in research with OIF/OEF/OND family members, using expert panel input and focus group interviews (71). We are using several of these outcomes and instruments in our two current military spouse studies and our REACH VA clinical program.

Category	Name of Measure/Form	Battery (B) Screening (S)
----------	----------------------	------------------------------

		Risk Priority Inventory (RPI)
Depression	Patient Health Questionnaire (PHQ-9)	B
Anxiety	Generalized Anxiety Disorder (GAD-7)	B
Burden	Zarit Burden Interview (ZBI) short version	B
Caregiver self-efficacy	Revised Scale for Caregiving Self-Efficacy	B
Safety concerns	General questions	RPI
Caregiving frustrations	Frustrations questions	RPI
Time spent in caregiving	Caregiver Vigilance Scale	RPI
Social support	Satisfaction and someone to take over	RPI
Health behaviors	General questions	RPI
Patient disability status and rating	General questions	RPI
Demographics	Participant and service member demographics	B
Social support	Received support, negative interactions, satisfaction, and social networks	B
Health	SF 36	B
Patient functioning and disability	World Health Organization Disability Assessment Schedule 2.0 (WHODAS 2.0)	B
ADLs	Katz ADL Scale	S, B
IADLs	Lawton and Brody IADL Scale	S, B
Financial strain	Economic Strain Scale	B
Career impact	General questions	B
Caregiver strain	Caregiver Strain Index	B
Life Stress events	Social Readjustment Rating Scale	B
Relationship quality	General questions	B
Impact on children	Impact of Caregiving on Family Life	B

## Independent Measures.

**Risk Priority Inventory.** The Risk Priority Inventory (RPI), adapted from REACH (79), is collected by the RA as part of data collection and a copy given to the Interventionist who will review it with the caregiver to use as the basis for discussion of concerns and intervention targeting. Measures assessing the outcomes are also provided to the Interventionist. The RPI assesses caregiving risk areas of education, safety, health and healthy behaviors, social support, and caregiving frustrations. Safety questions will examine service member access to dangerous objects, driving, and risky behaviors and are scored from 0 (never) to 2 (often). Higher scores indicate greater safety risk. Caregiver's self-care and preventive health behaviors (e.g., getting enough rest, keeping medical appointments, smoking) will be assessed using four REACH II questions (36). All self-care items are scored 0 or 1 (no or yes), and summed 0 to 4. Higher scores indicate increase health risk. Three social support items assess satisfaction with help and emotional support and whether the caregiver had someone to take over care if needed. Satisfaction items are scored 1 (not at all) to 3 (very). Higher scores indicate increased social support risk. Two items assess caregiver frustrations (e.g., feel like yelling at or hitting patient). Items are scored from never (0) to often (2). Higher scores indicate more frustrations (41). Service member disability status and rating from the VA or DoD will also be collected (23). Caregiving time spent on duty and in care activities in hours and minutes per day will be assessed with two questions from the Caregiver Vigilance Scale questions. Cronbach's alpha for the 4-item scale is .66 (80). In addition to the RPI items, depression, anxiety, and burden measures are provided to the Interventionist to use in targeting concerns for the dyad.

Demographics for caregiver and care recipient will include name; date of birth; age; gender; race/ethnicity; marital status; years married; relationship to service member; employment status; number of people in household, ages and relationships; income (categories by income/month); and military service; time and era of service; branch of service, age, rank, time in military, and previous deployments.

Caregiving self-efficacy will be measured by the Revised Scale for Caregiving Self-Efficacy (81,82). The 15-item scale has three subscales (five items per subscale), self-efficacy for obtaining respite (SE-OR), self-efficacy for responding to disturbing behaviors (SE-RDB), and self-efficacy for controlling upsetting thoughts (SE-CUT). Participants rate their level of confidence to perform each item on a scale from 0 (cannot do at all) to 100 (certain can do). Subscale scores are reported separately. In a Chinese sample, Cronbach's  $\alpha$  for SE-OR, SE-RDB, and SE-CUT were 0.91, 0.96, and 0.96, respectively (83).

Social support is an important buffer against stress for caregivers and a family resilience factor (53). More than half of post 9/11 military caregivers have no caregiving network (23). We will examine social support using questions from instruments utilized in several previous REACH studies (84-87). Nineteen social support items measure received support and negative interactions (85), satisfaction (85,86), and social networks (87). The first three domains use a scale of 0 (never, not at all) to 3 (very often, very). Social network items use a scale of 0 (none) to 5 (9 or more). For total social support items' sum, 0 through 69, higher scores indicate more support. A study of 1103 U.S. older people yielded Cronbach's alphas of .84 for received support (88), .71 for support satisfaction (89), and .83 for negative interactions (90). Social networks had a Cronbach's alpha of .83 in a European validation study of 7432 older people (91).

Health will be assessed from 1 (poor) to 5 (excellent) with one question from the Medical Outcomes Study 36-Item Short-Form Health Survey (SF-36) (92). Relationship quality will be assessed with a four item measure (93) used in the Rand caregiving study (23) that assesses closeness, communication, similarity, and general relationship. Items are rated on a five point scale from 1 (not at all) to 5 (extremely) and averaged.

Financial strain will be measured with two Economic Strain Scale (94) items. Participants rate how much difficulty the household had paying bills in the past six months on a scale from 1 (no difficulty) to 4 (a great deal) and whether the household has enough money to afford housing, food and clothes you feel you

should have, on a scale from 0 (definitely enough) to 3 (definitely not enough). Further economic impact on the caregiver's career will be examined by seven questions taken from the National Alliance for Caregiving, also used in the Rand military caregiver study (23). These items (e.g., take unpaid time off, take early retirement) will be scored either 0 (no) or 1 (yes). Caregiver strain (e.g., physical, work, family) will be measured using the 12 item Modified Caregiver Strain Index (95,96). Responses are coded 0 (no), 1 (yes, sometimes), or 2 (yes, on a regular basis) and summed. Reliability is .90 and test-retest reliability coefficient is .88 (96).

At screening, care recipient function will be assessed using the 6-item Katz ADL Scale (97) and 8-item Lawton and Brody IADL Scale (98). Each item is scored 0 (no help needed) or 1 (help needed). ADL and IADL items are summed separately, with higher scores indicating greater impairment. Cronbach's alpha is .75 across three studies for ADL (99) and IADL averaged .84 in multiple study review (100).

The World Health Organization Disability Assessment Schedule 2.0 (WHODAS 2.0) (101) provides a measure of impairment because of military or health-related problems, can be used across diseases, including mental, neurological and addictive disorders, is culturally neutral, and produces standardized disability levels and profiles. It is based on the International Classification of Functioning, Disability and Health and is one of the scales recommended for use in assessing PTSD disability (102). There is a proxy version, which will be used in this study to ask participants about the service member's functioning. The scale provides a profile of functioning across 6 activity domains, understanding and communicating, mobility, self-care, interpersonal, work and household, and participation in society, and a general disability score. In research on participation after TBI, proxy report has been shown to be an acceptable substitute for missing participant report on productivity and community activity outcomes (103). In the WHODAS 2.0 12 +24 version, positive responses to the 12 core items (which explain 81% of variance of the more detailed 36-item version) trigger further questions. Items are scored as level of difficulty within the past 30 days from 1 (none) to 5 (extreme or cannot do). Scoring takes into account multiple levels of difficulty for each item, coding each item response separately, and uses an algorithm to determine the summary score by differentially weighting the items and the levels of severity. Summary score ranges from 0 (no disability) to 100 (full disability).

The Social Readjustment Rating Scale (SRRS) is a list of 43 stressful life events, both positive and negative, that can contribute to illness (104). Twelve of these events that we have used before and are most likely for this age cohort will be measured, such as change in employment or financial state. Occurrence of the event in the last six months is scored as no (0) or 1 (yes). Each event has points assigned to it based on how stressful it is. Points for all events present are added for a total score that ranges from 0 to 437.

For those parents who have younger children or are taking care of grandchildren, a six-item measure from the Rand military caregivers study (23) will examine how caring for the patient has changed the family. A scale of 1 (strongly disagree) to 5 (strongly agree) will be used with higher scores indicating more impact.

**Project Evaluation.** Participant satisfaction, collected at final follow-up as part of project evaluation, will assess participant perception of satisfaction, usefulness, benefit, and relevance.

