The strength of the individual sessions intervention is that it is structured, standardized and targeted to help caregiver focus on what needs to be done in the short and long term, without being overwhelmed by the many challenges of care. The sessions are structured through a protocol that specifies activities to occur at each session. There are materials for staff in an Interventionist Manual including protocols, and scripts and talking points for each topic. The intervention is standardized to ensure that the five caregiving risk areas of safety, social support, problem behaviors, caregiver emotional well-being, and caregiver health are covered and core skills are taught.

Most importantly, however, the intervention is targeted and individualized to the concerns of the specific caregiver and care recipient through a risk assessment. The Risk Priority Inventory (RPI) assesses the main caregiving risk areas for the specific caregiving dyad. The RPI is used to tailor the intervention for care recipient behaviors or safety issues and/or caregiver centered issues/concerns related to health, physical and emotional well being, and/or social support.

The individual sessions incorporate evidence-based components that are crucial to successful caregiving interventions (36,21,37) including problem solving, cognitive restructuring/mood management, and stress reduction. The Interventionist and caregiver negotiate the concerns to be addressed using those identified by the risk assessment. Using problem solving techniques, Interventionist and caregiver attempt to find effective and workable solutions to a specific target behavior/issue that is causing stress and burden for the caregiver. The target behavior/issue could be something related to the caregiver, such as asking family members for help, or to the care recipient, such as bathing or driving. In this way the intervention accommodates whatever concern the caregiver is experiencing – from ADL challenges for seriously compromised service members to risky behaviors of service members with mild TBI or PTSD, or to caregiver stress, guilt or grief.

The Interventionist teaches the ABC (Antecedent, Behavior, Consequences) method of problem solving and the caregiver and Interventionist identify action-oriented behavioral strategies to address caregiving problems or patient behaviors using topics from the Caregiver Workbook in a targeted behavior/issue plan. Problem solving steps include:

1. Determine problem

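### The Risk Priority Inventory satisfaction items are coded against their own risk label, so as written the most satisfied caregiver gets the highest social support risk score.

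*Combined protocol and SAP*

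**What the plan says.** The RPI is described in Independent Measures as a set of short item groups, each with its own coding and direction.

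- Social support: "Three social support items assess satisfaction with help and emotional support and whether the caregiver had someone to take over care if needed". The coding follows: "Satisfaction items are scored 1 (not at all) to 3 (very). Higher scores indicate increased social support risk". No coding is given for the take-over item, and no rule is given for combining the three items.
- Self-care: "All self-care items are scored 0 or 1 (no or yes), and summed 0 to 4. Higher scores indicate increase health risk". The example topics are "e.g., getting enough rest, keeping medical appointments, smoking". The four questions are taken from an earlier trial and are not reproduced.
- Safety: the items "are scored from 0 (never) to 2 (often). Higher scores indicate greater safety risk".
- Frustrations: two items, also coded 0 (never) to 2 (often), with higher meaning more frustration.

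The RPI has two uses. In Interventions and Materials (Individual Sessions Arm), "The RPI is used to tailor the intervention for care recipient behaviors or safety issues"; the same sentence goes on to caregiver health, well-being and social support. It is also collected by the Research Associate as part of study data and is listed among the independent measures.

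**The concern.** The sentence that sets the satisfaction anchors and the sentence that sets the direction cannot both hold without a reversal, and no reversal appears anywhere in the documents. This is more than missing detail: a rule is stated, and following it gives the opposite of what its label says.

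Two uses are exposed. First, an Interventionist or analyst who takes a high support score at its stated meaning would see risk where the caregiver reports satisfaction. Second, the Mixed-Effects Modeling Approach lists the caregiver's general social support as a covariate of interest without naming the instrument, and the measures table lists two social support measures. If the RPI items were used under their stated label, the sign of the association would be misread.

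The self-care rule raises a narrower question. A uniform yes = 1 code cannot make a sum rise with risk if some items ask about protective behaviours and others about harmful ones.

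**Working it through.** All coding inputs come from the RPI paragraph of Independent Measures.

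**1. The plan's own figure.** The only total range given for an RPI group is self-care, 0 to 4. Four items scored 0 or 1 give 4 × 0 = 0 to 4 × 1 = 4. It reproduces.

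**2. Satisfaction items.** The number of satisfaction items, k, is not stated outright. The wording suggests k = 2 (help, emotional support) plus one take-over item; k = 3 is the upper case. As written the score is k × x; reversed it is k × (4 − x).

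| Caregiver | x | As written, k = 2 | As written, k = 3 | Reversed, k = 2 | Reversed, k = 3 |
|---|---|---|---|---|---|
| Not at all satisfied | 1 | 2 | 3 | 6 | 9 |
| Very satisfied | 3 | 6 | 9 | 2 | 3 |

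As written, the maximum, labelled highest risk, belongs to the very satisfied caregiver, whichever k applies. After reversal the order agrees with the label.

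**3. Take-over item.** With no stated coding, neither its direction nor that of the three-item set can be computed.

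**4. Self-care, on the assumption that items are worded like the example topics.** Using the three named topics (rest, appointments, smoking):

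- Rests, keeps appointments, does not smoke: 1 + 1 + 0 = 2 as written. With the protective items reversed: 0 + 0 + 0 = 0.
- Does neither and smokes: 0 + 0 + 1 = 1 as written. With the protective items reversed: 1 + 1 + 1 = 3.

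The fourth item is not shown. It adds 0 or 1, so as written the first profile totals 2 or 3 and the second 1 or 2. The healthier profile is never ranked at lower risk, and at best the two tie. If the items are instead worded as risks (for example, not getting enough rest), yes = 1 is already right and there is no fault.

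**5. Safety and frustrations.** Both run from never (0) to often (2), with higher meaning more of the problem. They are consistent.

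**6. Effect in a model.** Replacing x by 4 − x is linear. In a model with a satisfaction score as covariate, the reversal changes the sign of its coefficient and shifts the intercept. Fit is unchanged, so the error would lie in interpretation and not in the estimated difference between arms.

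**The case against.** The strongest reply is that this is a wording slip with little practical effect. The Interventionist receives a copy of the RPI and goes through it with the caregiver; the two then negotiate which concerns to address. Session 1 also asks the caregiver to tell their story. A caregiver who answers that they are very satisfied, and is then asked about it, is unlikely to be treated as lacking support. The Statement of Work leaves the data forms to be finalised in the Manual of Operations, so a reversal may exist in forms or syntax that are not shown. The RPI is neither an outcome nor a power input, and a separate 19-item support measure (0 to 69, higher meaning more support) is available for analysis.

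Most of this stands, and it limits the consequence. It does not remove the contradiction: anyone scoring from this text would score satisfaction backwards. Concerns are negotiated from those the risk assessment identifies, so the direction of its scores still matters. The 19-item measure is labelled in the opposite direction to the RPI score, which makes a mix-up easier.

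The objection on self-care also stands in part. The wording of the four questions is not visible, so a fault there is conditional.

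A reader might infer more: that the whole RPI runs backwards, that sessions will be aimed at the wrong areas, or that the data cannot be interpreted. The documents do not support any of these. Safety and frustrations are coherent. No cut-off, ranking or algorithm selects session targets. Recorded item responses can be recoded without loss at any time.

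**Conclusion.** The point holds for the satisfaction items without further assumption: anchors and stated direction conflict, and the reversal covers the whole 1 to 3 range. For self-care it holds only if the protective items are worded positively, and then the fault is mixed direction, not full reversal. For the take-over item the coding is simply absent.

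The consequence is modest. It concerns the meaning of the RPI support score as a targeting aid and as an independent variable. Mis-targeting is possible but not shown. Depression, anxiety and burden, which are the outcomes and the only inputs to the power table, are not directly affected. An unstated reversal step is a plausible explanation, but the documents do not confirm it.

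**What to change.** In the RPI paragraph of Independent Measures:

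1. State that satisfaction items are reverse-coded as 4 minus the score before being read as risk, or correct the direction sentence to say that higher means more satisfaction. Do one, not both.
2. State the coding of the take-over item so that having no one to take over is the risk response, and say whether the three items are combined.
3. Check the wording of the four self-care items. Reverse-code (1 minus the score) only those that ask about a protective behaviour in positive terms, then sum. Reversing items already worded as risks would create the fault.
4. Check that the data form, the scoring syntax and the Interventionist's copy follow the same rule.
5. In the Mixed-Effects Modeling Approach, name the instrument behind the social support covariate and its direction.

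Safety and frustrations need no change. The cost is one paragraph and a few lines of syntax. No new data are needed, and item responses already recorded can be rescored.

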## **Data Analysis**

Primary outcomes are measured for all participants at baseline, at three months, and after six months. We estimate the necessary sample size based on analysis of a pretest-posttest control group design. The final analysis of the data will, in addition to this approach, use a mixed-effects model. These models allow us to assess whether other factors, such as a participant's age or the patient's level of disability, are related to the measured outcomes.

Randomization will likely lead to slightly different group sizes in the study arms because participants are independently assigned to the arms, but we are not concerned about this as group sizes will also be different due to expected drop outs in each group. Once assigned to a study arm, participants will be considered in the study and we will primarily follow an intention-to-treat (ITT) approach, both for ANOVA and the mixed-effects modeling approach described below. Individuals will be included in their assigned group even if they do not participate in some or all of the intervention components (i.e., does not comply with the “treatment”).

The benefit of ITT is twofold. First, we do not bias the result by defining “sufficient compliance” with the treatment/intervention after data are collected. Second, we assure that our study result is relevant in the sense that any effect of the intervention is actually achievable with the level of encouragement to stay in the intervention as provided in this study. Especially, potential future benefits from the intervention will *not* be conditional on future participants who comply fully with the advised meetings and exercises, even in case many individuals have difficulties in study compliance.

Having said that, we will record the level of participation for each individual in each intervention arm (number of sessions that the individual participated in), and we will investigate the importance of this compliance. We expect that compliance will be an important indicator of how engaged an individual was, and how much of the offered support or education an individual could benefit from. This is an exploratory part of our data analysis.

A second data analysis strategy will be to analyze data for only those participants who complete the study, which is an efficacy analysis. This introduces a self-selection bias, and statistical power is diminished by loss to follow-up during the course of the study. However, our estimates of treatment effects are unbiased by random attrition. The chief advantage of this primary data analysis strategy is that it has increased ability to document positive findings for participants able to maintain compliance with the intervention. However, when analyzing efficacy it is especially important to document any differences between participants who completed the study and those who were either withdrawn or lost to follow-up. Baseline demographic and clinical characteristics will be compared between completers and non-completers using chi-square tests for contingency tables, or independent-samples t-tests, as appropriate.

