The values tabulated in the Detectable Difference column of the table document the minimum true between contrast group difference in gain scores in population data sampled needed for statistical power to attain 0.80 or better to reject a false null hypothesis of no group by time interaction effect in repeated measures data. In general terms, we will have statistical power of 0.80 or better to reject a false null hypothesis when the between contrast group difference in gain scores attains approximately 0.30 or more of the population standard deviation estimated from REACH and READI study baseline data. For statistically significant comparisons, effect size of  $d \geq 0.2$  will be considered clinically significant, consistent with psychosocial interventions' small to medium effect sizes (46). Interaction effect sizes will be estimated as mean between-group gain score change relative to estimated population standard deviation (106).

**Mixed-Effects Modeling Approach.** Randomization into the two arms, respectively, guarantees that individuals are not systematically assigned to one arm. Regardless, when analyzing the data it should be beneficial to account for the actually present covariates for the individuals. In addition, the mixed-effects modeling approach allows us to incorporate individuals in the study who are lacking the final outcome measurements after six months. Furthermore, we can utilize all the information from the data and can utilize the post-intervention measurements for the individuals.

We will fit separate mixed-effects models for each of the primary outcomes. For each of the  $i = 1, \dots, 160$  individuals there are  $n_i$  measurements available (for a specific outcome). The primary outcomes are measured at baseline (B), and after three, and six months ( $t = B, 3, 6$ ). It is not essential that the measurements are taken for all individuals at the same time, but we do not elaborate on this here because the data collection is planned to follow the above timeline. If all measurements are available for an individual,  $n_i = 3$  (for each primary outcome). Each individual will have measurements for at least baseline, so  $n_i \geq 1$  for all  $i$ . In mixed-effects models "individuals borrow strength" from each other and it is therefore not required that all individuals have two or more measurements in order to fit straight lines to each individual.

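### The efficacy analysis is defined by completing the study, not by attending sessions, so it does not estimate an effect in compliers; and the ANOVA's ITT label has no missing-outcome method behind it

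*Combined protocol and SAP*

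**What the plan says.** In Data Analysis, the main approach is ITT: "we will primarily follow an intention-to-treat (ITT) approach, both for ANOVA and the mixed-effects modeling approach described below". The rule that follows concerns participation only: "Individuals will be included in their assigned group even if they do not participate in some or all of the intervention components". Session counts are recorded for each participant, and their role is examined in an exploratory analysis.

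The next paragraph adds the completer analysis: "A second data analysis strategy will be to analyze data for only those participants who complete the study, which is an efficacy analysis". Its counterpart group is shown by the planned baseline comparison, between "participants who completed the study and those who were either withdrawn or lost to follow-up". The plan concedes a drawback: "This introduces a self-selection bias, and statistical power is diminished by loss to follow-up during the course of the study". It then says the estimates are not biased by random attrition and gives as the chief advantage of this strategy, now called primary, that "it has increased ability to document positive findings for participants able to maintain compliance with the intervention".

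Sample Size and Statistical Power bases the ANOVA on a pretest-posttest gain score, tested as a group-by-time interaction, with complete data on at least 60 caregivers per arm. Under the mixed-effects heading it says that "the mixed-effects modeling approach allows us to incorporate individuals in the study who are lacking the final outcome measurements after six months".

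**The concern.** The analysis is defined by one event (finishing the study) and its benefit is claimed for another (keeping up the intervention). If these can come apart, a result reported as efficacy in compliers would describe a different, self-selected group. The double ranking as second and primary leaves room for that result to be presented as the main one.

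A related gap affects the ITT label. Keeping non-attenders in their assigned arm settles who belongs to which group. It does not settle what happens when the outcome is missing. An ANOVA that omits people without a posttest is not an analysis of everyone randomised, whatever its label.

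**Working it through.** **1. The plan's own figure.** Inputs from Table 2: SD and reliability r are 5.94 and 0.84 (PHQ-9), 5.14 and 0.83 (GAD-7), 9.74 and 0.88 (Zarit). Detectable differences are 1.78, 1.54 and 2.92. Alpha is 0.05, two-sided, and power 0.80.

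SD of gain = SD × √(2(1 − r)); n per arm = 2(1.96 + 0.84)² × (SD of gain)² / difference².

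| Outcome | SD of gain | n per arm | Power at 60 | Power at 80 |
|---|---|---|---|---|
| PHQ-9 | 3.360 | 56 | 0.827 | 0.918 |
| GAD-7 | 2.997 | 60 | 0.804 | 0.901 |
| Zarit | 4.772 | 42 | 0.918 | 0.972 |

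The largest requirement is 60, so the plan's figure is reproduced. With 20% loss, 80 × 0.80 = 64, so at least 60 is true as a floor. The stated ANOVA power is thus power for people with complete data, not for all 80 per arm.

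**2. Completion against compliance.**

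| | Attending sessions | Completing the study |
|---|---|---|
| Timing | Individual arm: six telephone sessions within three months (Individual Sessions Arm) | Data calls at baseline, 3 and 6 months from randomisation (Data Collection) |
| Conducted by | Interventionist | Research Associate, with $25 for each completed call (Retention) |
| Effect of skipping sessions | Lower session count | None: the person stays in the assigned group (Data Analysis) |
| Recorded as | Session count, exploratory | Completer, as against withdrawn or lost |

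On this reading, someone who attends nothing but answers the calls is a completer. Someone who finishes all six sessions and then misses the six-month call is not.

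**3. The ANOVA.** A gain score needs a posttest. No imputation or other rule for missing outcomes is given, so anyone without a posttest drops out. If the posttest is month 6, the remaining people are essentially those of the completer analysis. If it is month 3, the two sets can differ, but people without a month-3 value are still lost.

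**4. How mixed the completer set could be (assumed inputs).** Let p be the share keeping up the sessions, a the retention among them, and 0.80 overall retention (the plan's 20% loss). The share of completers who did not keep up the sessions is 1 − a × p / 0.80. With p = 0.70:

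- a = 0.80: 1 − 0.56/0.80 = 30%
- a = 0.90: 1 − 0.63/0.80 = 21%
- a = 1.00: 1 − 0.70/0.80 = 12.5%

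Over p from 0.50 to 0.90 and a from 0.80 to 1.00, where feasible, the share runs from 0% to 50%.

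**5. What this could do to the estimate (assumed inputs).** Of 80 in the Individual Sessions arm, let 56 adhere with an effect of 0.40 SD and 24 not adhere with none. Let 6 adherent and 10 non-adherent people be lost.

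- Completers: 50 + 14 = 64, of whom 14/64 = 22% are non-adherent
- Completer estimate: 0.40 × 50/64 = 0.31 SD
- ITT: 0.40 × 56/80 = 0.28 SD
- Adherent people left out: 6/56 = 11%

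This takes webinar-arm completers to have the same mean as everyone in that arm.

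**6. Loss that is not random (assumed mechanism).** A simulation used the PHQ-9 inputs, a true difference of 1.78 and about 20% loss per arm. Loss was random in the webinar arm and more likely after a poor three-month change in the Individual Sessions arm. The mean gain-score difference was 1.78 in all randomised and 2.01 in completers, an excess of 0.23 points (0.23/1.78 = 13%). The statement about unbiased estimates therefore holds only if attrition is in fact random.

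**The case against.** The strongest reply is that the plan already protects its main conclusion. ITT leads, self-selection and lost power are admitted, the mixed model keeps people without a final outcome, and session counts are analysed elsewhere (as webinar dosage, and in the Hypotheses section as a variable to control for). What remains is the label and rationale of a supporting analysis. This largely stands, and it is why the point is not about the trial's validity.

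A reader might also infer more than the text supports:

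- **That the set is simply those who answered the last call.** The plan never defines completing the study. The contrast with withdrawal and loss supports that reading but does not prove it. If completion meant sessions, the set would still be selected after randomisation.
- **That the ITT ANOVA and the efficacy ANOVA are the same analysis.** The posttest month is not named and deletion of incomplete cases is not stated, so this holds only conditionally.
- **That the dropout comparison is pooled over arms and cannot detect differential loss.** The text does not say whether it is pooled or by arm, and the last paragraph of the plan also promises to explore dropout patterns.
- **That the distortion is large.** In the illustration the completer and ITT estimates differ by only 0.03 SD, and every input except the arm size and the 20% loss is assumed.

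**Conclusion.** The concern holds in a limited form. The completer analysis has no session threshold and is selected after randomisation, so it does not support a claim about people who maintain compliance. Its ranking contradicts the ITT statement just before it. The ITT label on the ANOVA is not backed by any handling of missing outcomes; the overlap with the completer set is essentially complete only if the posttest is month 6. The mixed model is not affected, subject to its stated missing-at-random assumption.

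The size cannot be read from the documents. Under the assumptions shown, non-adherent people could make up 12.5% to 30% of completers, and the estimate could fall short of the effect in adherent people (0.31 against 0.40 SD) or overstate the effect in all randomised (2.01 against 1.78 points). This is a defect of definition and estimand that should be corrected; the sample size stands.

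**What to change.** In the completer paragraph of Data Analysis:

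- Define completing the study, and call this a complete-case sensitivity analysis.
- Delete the efficacy, compliance and primary wording.
- Limit the statement about unbiased estimates to the case where attrition is random.

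In the ITT paragraph, state that the ITT result comes from the mixed model under missing at random, and that the ANOVA is complete-case.

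Report dropout rates and baseline characteristics of completers and non-completers by arm, descriptively. A formal test of whether the differences vary by arm would say little. With 16 lost and 64 kept per arm, its standard error is √(2(1/16 + 1/64)) = 0.40 SD, so 80% power needs a difference of about 2.8 × 0.40 = 1.1 SD. Last observed scores should not be used for this comparison, because they mix time with dropout.

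Keep any session-count analysis exploratory, with adherence defined before outcomes are seen by arm and the assumptions stated. A complier-average effect is not a ready substitute. It needs assignment to have no effect in non-adherers, which partial attendance and webinars offered only to the control arm make doubtful.

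Cost: wording changes and a little extra tabulation, with no new data. The plan gives up a result labelled efficacy.
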